12.2.4 Safety evaluation

AEs will be evaluated considering frequency and intensity. Furthermore, AEs will be evaluated considering relationship to the IMP, outcome, and seriousness. Both will be described by absolute and relative frequency. Descriptive statistics will be calculated for clinical laboratory parameters determined. Frequencies of values inside and out of normal range (i.e. above and below) will be given where possible.

13 RECORD KEEPING

The investigator will maintain adequate and accurate records to enable the conduct of the trial to be fully documented and the trial data to be subsequently verified according to the international legal requirements or according to the local applicable regulatory requirements.

13.1 Documentation of patients' participation

Patient clinical source documents include, but are not limited to, patient clinic records, physician's and nurse's notes, appointment book, original laboratory reports, imaging diagnostic, pathology and special assessment reports, consultant letters, etc.

13.2 Data protection

13.3 Essential documents at trial center

Essential documents related to the clinical trial will be retained in the Trial Master File and patient clinical source documents.

The Trial Master File will contain the clinical protocol/protocol amendments, sample of eCRF printout, ECs/IRB and regulatory authorities' approval with correspondence, original initialed and dated PI as well as the signed IC, sample PI sheet and IC form, trial medication records, investigator's curriculum vitae and authorization forms, screening and enrollment logs, and other appropriate documents/correspondence as per ICH-GCP and local regulations.

13.4 Archiving

Documents must be kept on file by the investigator for 15 years. If source documents are not durable as long as needed (e.g. printouts on thermo labile paper), they must be preserved as certified copy.

14 QUALITY ASSURANCE

Domestic and foreign regulatory authorities, the ECs/IRB, and an authorized auditor may request access to all source documents, CRF, and other trial documentation for on-site audit or inspection. Audits and inspections can be conducted at any time during or after the trial to assure the validity and integrity of trial data.

Direct access to these documents must be guaranteed by the investigator, who must provide support at all times for these activities. Medical records and other trial documents may be copied during audit or inspection provided that patient names are obliterated on the copies to ensure confidentiality.

15 LEGAL AND BUSINESS MATTERS

15.1 Insurance for patients

Liability and insurance provisions for patients will be arranged according to legal requirements. In accordance with the applicable national laws of each participating country and GCP, the sponsor has effected a patient insurance. The investigator will receive a copy of the insurance certificate as well as of the corresponding insurance conditions prior to the start of the study. Following the clauses of the contract, the patients have to be informed about the existence of the insurance contract and about their obligations.

Liability and insurance provisions for patients and investigators participating in this trial are given in separate agreements.

15.2 Contracts, finances

Before the start of the trial, the investigator will disclose any proprietary or financial interests he or she might hold in the investigational products as outlined in a 'financial disclosure form' prepared for this trial. The investigator agrees to update this information in case of significant changes during the trial. Similar information will be provided by each sub-investigator to whom the investigator delegates significant trial related responsibilities.

15.3 Disclosure of all information and results

All information concerning the results derived from the trial and the investigational product are regarded as confidential. The investigators and members of their research teams are not permitted to disclose any such information without prior written approval as long as the data are unpublished. By his signature the investigator(s) agree(s) to keep the data confidential.

16 REGULATORY AND ETHICS

16.1 Good Clinical Practice

This trial is to be conducted according to globally accepted standards of GCP (as defined in the ICH E6 R2 Guideline), in agreement with the Declaration of Helsinki from 2013 and in keeping with local regulations. The investigator should ensure on an ongoing basis that all persons assisting with the trial are adequately qualified, informed about the protocol, any amendments to the protocol, the trial treatments, and their trial-related duties and functions. Minutes of trial team meetings and documentation of trial team training should be maintained in the trial investigator site file.

The investigator should maintain a list of sub-investigators and other appropriately qualified persons to whom he/she has delegated significant trial-related duties.

Serious GCP breaches or serious protocol deviations mean a breach likely to affect to a significant degree the safety and rights of a patient or the reliability and robustness of the data generated in the clinical trial.

16.2 Subject information and informed consent

Every trial participant will receive a complete and comprehensive explanation of the significance, nature, extent and possible risks of the trial. To this end a detailed, written sheet will be made available. In addition, the investigator will carry out an oral information session during which the patients will be given sufficient time and opportunity to clarify remaining questions. The investigator has to document his/her conversation with the patient with date, duration of the conversation, main contents, questions and answers in patient's medical file. In addition, the investigator has to document in the patient's file that the patient is enrolled into the trial.

The investigator will inform the patient or his/her legal representative(s) that his/her consent to participation can be withdrawn at any time without giving any reason and that no disadvantages will result concerning further medical treatment. Neither the investigator nor the site staff should coerce or unduly influence a patient to participate or to continue to participate in the trial.

The patient information sheet has to be initialed and dated by the patient and/or his/her legal representative(s) to confirm comprehension. Afterwards, the patient and the investigator will sign and date the Informed Consent form personally. The original initialed and dated patient information as well as the signed Informed Consent Form will be archived in the Trial Master File. The patient will receive the second original of the patient information and signed Informed Consent Form.

The investigator is responsible for correctly obtaining the Informed Consent in accordance with the applicable regulatory requirement(s), GCP and the ethical principles that have their origin in the Declaration of Helsinki. A signed Informed Consent form must be obtained prior to initiation of any trial-specific procedures. Date and time of signature must be documented. The record of the Informed Consent must be available for an audit by competent authorities (CAs) whenever requested. The patient will be informed about any changes in the trial protocol due to substantial protocol amendments and will be asked to sign an amended patient information sheet and Informed Consent form accordingly.

17 PUBLICATION POLICY

Publication of trial results requires a mutual agreement between the investigator(s) and Bionorica SE. Any publication of the trial data by the sponsor or investigator(s) will wholly be consistent with the integrated report in accordance with the ethical principles of the Declaration of Helsinki.

TITLE PAGE

STATISTICAL ANALYSIS PLAN

Of Multicenter, Randomized, Open-Label, Comparative Study of Therapeutic Efficacy, Safety and Tolerability of Imupret application in the therapeutic concept of delayed prescription of antibiotics in children, aged 6-12 with severe acute tonsillitis.

Working Title:

ATi-2

Imupret in tonsillitis

Clinical phase: IV

Date: 07.02.2019

Name of the investigational product: Imupret®

Coordinating Investigator: [name]. [name]

Sponsor:

Ivano-Frankivsk National Medical University

[name]. [name]

[name]

Statistical evaluation

The statistical planning of the trial and the statistical analyses will be conducted following the principles specified in the ICH Topic E9 (ICH, 1998), and will be carried out by a qualified statistician in accordance with the ICH. Technical details of the statistical analyses will be specified prior to data analyses.

In general, there will be one main statistical evaluation.

Data base will be closed after all data are entered and cleaned.

In general, unless otherwise stated, continuous data will be summarized by means of descriptive statistics (mean, standard deviation (SD), median, quartiles, minimum, and maximum). Categorical variables will be described in contingency tables as absolute number and percentages.

AEs will be evaluated considering frequency and intensity. Furthermore, AEs will be evaluated considering relationship to the IMP, outcome, and seriousness. Both will be described by absolute and relative frequency. Descriptive statistics will be calculated for clinical laboratory parameters determined. Frequencies of values inside and out of normal range (i.e. above and below) will be given where possible.

This is an exploratory trial with no formal sample size estimation. Therefore, beneath descriptive statistics of efficacy endpoints, concluding statistics may be performed in a data driven way, in order to find clinically relevant differences between study participants, time points and treatments. Possible corrections to prevent an alpha inflation will be performed, if meaningful.

Specifications of the biometrical evaluation will be defined after all data management processes of the study phase will be terminated and data base was closed. In general, variables will be analyzed considering the underlying analysis set, treatment and time point, if meaningful.

Analysis sets

Full Analysis Set (FAS)

The FAS consists of all randomized patients with at least one documented application of IMP and with at least one observed post-baseline value.

Per Protocol Set (PPS)

The PPS consists of all patients of the FAS without major protocol deviations. The evaluation of protocol deviations and whether they lead to the exclusion of a patient from the PPS will be performed during data review of the study.

Primary endpoint

Main criterion for evaluation in the trial will be:

- Scores determined by the Local Tonsillitis Manifestations Scale refined by McIsaac's scale. Scores will be dichotomized to decide for two categories (therapy effective/therapy ineffective). Scores will be evaluated by treatment and time point, i.e. per visit
- Need for an antibacterial therapy, i.e. number of patients per treatment.

Secondary endpoints

- Scores/Intensity of each underlying disease symptom assessed by the Local Tonsillitis Manifestations Scale by treatment and time point, i.e. per visit
- Axillary temperature per treatment and measurement time point
- Patient's self-assessments on VAS per treatment and measurement time point
- Self-assessment of the symptoms by the patient.

Safety evaluation

AEs will be evaluated considering frequency and intensity. Furthermore, AEs will be evaluated considering relationship to the IMP, outcome, and seriousness. Both will be described by absolute and relative frequency. Descriptive statistics will be calculated for clinical laboratory parameters determined. Frequencies of values inside and out of normal range (i.e. above and below) will be given where possible.

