
Sample size calculation
	
Justification of the number of subjects
 
This trial is parallel, two-group, with the same size groups.
 
The planned test power is 80% (the probability of making a second kind error is 0.2), the two-way probability of making a type 1 error is 0.05. The sample size was estimated by the main variable of the clinical trial.
 
Thus, this trial was a comparative for superior efficiency.
 
When proving superior therapeutic efficacy, the following statistical hypotheses are tested:
 
H0: e £ d versus On: e > d, where d is the limit of greater efficiency — the marginal value of clinically important differences, at which it can be considered that the tested drug exceeds its effectiveness by control (in this study it was taken equal to 15%); e - estimated (observed) differences between groups in therapeutic efficacy.
 
Given that the main variable is dichotomous, the size of each group can be estimated using the following expressions:
 
n control = k · n main
 $n_{main} = \frac{(z_{\alpha} + z_{\beta})^2}{(\varepsilon - \delta)^2} \cdot \left[\frac{p_{control} \cdot (1 - p_{control})}{k} + p_{main} \cdot (1 - p_{main}) \right]$ 
where: z_{α} and z_{β} —the corresponding percentage points of the standard normal distribution; d - the minimum acceptable value of clinically important differences; e - presumed (observable) differences between groups on therapeutic efficacy (the difference between the shares of positive results in groups); pcontrol and p main —shares of positive results in the

main and control groups, respectively; k - coefficient for unequal number of patients in groups (control is greater than the main); n_{main} и $n_{control}$ - the planned number of patients in the main and control groups, respectively; α is the boundary value of the error of the 1st kind (level of significance); β - is the boundary value of the error of the second kind.

In the planned study, it was assumed that the number of patients in the main and control groups was the same ($k = 1$), the significance level was $\alpha = 0.05$ (two-sided); the boundary value of the error of the second kind is $\beta = 0.2$ (which makes it possible to achieve a research power of 80%). Baseline data and the results of calculations using the above formula are given in Table. 1.

Table 1 - Baseline and Sample Size Estimation Results

Statistical indicator	Value of the indicator
Multiplicity factor k	1

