8.2 Sample size estimation

The clinical trial is designed in order to obtain a valid description of the in vivo performance of the active (add-on) treatment of Imupret in comparison to the reference standard treatment alone. Endpoints are defined as exploratory endpoints. Depending of the data finally obtained, several exploratory descriptive and statistic evaluations will be performed, so that a biometricaly based sample size estimation is not necessary. However, in order to guarantee a sufficient sample size for exploratory analyses of the data captured, a sample size of N=200 will be included. Treatments will be assorted in a 1:1 ratio, i.e. N=100 will receive an add-on treatment with Imupret® and N=100 will receive the standard treatment only.

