12.2 Statistical evaluation

The statistical planning of the trial and the statistical analyses will be conducted following the principles specified in the ICH Topic E9 (ICH, 1998), and will be carried out by a qualified statistician in accordance with the ICH. Technical details of the statistical analyses will be specified prior to data analyses.

In general, there will be one main statistical evaluation.

Data base will be closed after all data are entered and cleaned.

In general, unless otherwise stated, continuous data will be summarized by means of descriptive statistics (mean, standard deviation (SD), median, quartiles, minimum, and maximum). Categorical variables will be described in contingency tables as absolute number and percentages.

AEs will be evaluated considering frequency and intensity. Furthermore, AEs will be evaluated considering relationship to the IMP, outcome, and seriousness. Both will be described by absolute and relative frequency. Descriptive statistics will be calculated for clinical laboratory parameters determined. Frequencies of values inside and out of normal range (i.e. above and below) will be given where possible.

This is an exploratory trial with no formal sample size estimation. Therefore, beneath descriptive statistics of efficacy endpoints, concluding statistics may be performed in a data driven way, in order to find clinically relevant differences between study participants, time points and treatments. Possible corrections to prevent an alpha inflation will be performed, if meaningful.

Specifications of the biometrical evaluation will be defined after all data management processes of the study phase will be terminated and data base was closed. In general, variables will be analyzed considering the underlying analysis set, treatment and time point, if meaningful.

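### A superiority test at two-sided 0.05 is sized in the synopsis, but the analysis is to be specified only after the open-label database closes, so the 5% error rate is not guaranteed

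*SAP*

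**What the plan says.** The documents give the trial two different standings.

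- **Superiority test.** The sample size part of Protocol section 5 (synopsis) states "Thus, this trial was a comparative for superior efficiency" and that "the two-way probability of making a type 1 error is 0.05". It sets 80% power and derives 97, then 100, patients per group. Protocol 6.1 and 6.3 hope for confirmation of high efficacy in support of national guidelines.
- **Exploratory.** The design line of the synopsis and Protocol 8.1 use this word. Protocol 8.2 says "Endpoints are defined as exploratory endpoints" and that a biometrical sample size is not needed. Protocol 12.2 says "This is an exploratory trial with no formal sample size estimation", and the SAP repeats it.

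On timing and choice of analysis, Protocol 12.2 and the SAP share the same sentences:

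- "Specifications of the biometrical evaluation will be defined after all data management processes of the study phase will be terminated and data base was closed";
- "concluding statistics may be performed in a data driven way";
- "Possible corrections to prevent an alpha inflation will be performed, if meaningful";
- "Technical details of the statistical analyses will be specified prior to data analyses".

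Protocol 8.4 states that there is no blinding. Protocol 12.2.2 and the SAP list two main criteria: a dichotomised tonsillitis score evaluated at each visit, and the need for antibacterial therapy. Neither document names a test, a decision visit, an order for the two criteria or a multiplicity method.

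**The concern.** A two-sided 5% error rate belongs to one test fixed in advance. Here the test, the visit and the weight given to each main criterion may all be settled after closure of a database in which treatment is known. A p-value chosen that way need not have the stated error rate, and a reader cannot tell how many alternatives were open.

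The unresolved status of the trial matters as well. Read as a superiority trial, it has no protected test. Read as exploratory, its superiority hypothesis and power statement have no planned analysis behind them. The same data would support different conclusions under the two readings.

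**Working it through.** **1. Reproduce the plan's sample size.** Inputs from Table 1 of the synopsis: control rate 0.75, Imupret rate 0.90, z values 1.96 and 0.84, equal groups.

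- Variance term: 0.75 × 0.25 + 0.90 × 0.10 = 0.2775.
- n = (1.96 + 0.84)² × 0.2775 / 0.15² = 96.7, rounded up to 97 per group. Adding 3 for dropout gives 100.
- The same formula at one-sided 0.05 gives 76.3, so 77. The printed 97 therefore belongs to a two-sided 5% test.
- The denominator is 0.15², the distance between a true difference of 0.15 and zero, so 97 fits a test of no difference. The synopsis writes the hypothesis as a difference exceeding a margin of 0.15. With rates of 0.90 and 0.75 the true difference equals that margin, and power would be 2.5% at any sample size.
- Power at 97 per group: Φ(0.15 / √(0.2775/97) − 1.96) = Φ(0.844) = 80.1%.

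**2. Count the main tests left open.** Protocol 8.5 and 10.4 score the local scale at visits 2 and 4. Visit 3 is normally a telephone call with VAS only (Protocol 8.5, 10.3). Two score comparisons plus antibiotic need make 3 tests. This count is an assumption, because the documents set no limit.

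**3. Chance of at least one false positive with no correction.** For independent tests this is 1 − 0.95³ = 14.3%. Counting only errors favouring Imupret it is 1 − 0.975³ = 7.3%. For correlated tests I integrated over equally correlated normal statistics. The correlations are assumed.

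| Correlation | Any false p < 0.05 | Favouring Imupret (nominal 2.5%) |
|---|---|---|
| 0 | 14.3% | 7.3% |
| 0.3 | 13.6% | 6.8% |
| 0.5 | 12.5% | 6.3% |
| 0.7 | 10.9% | 5.5% |
| 0.9 | 8.4% | 4.2% |

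With visit 3 scored as a fourth test, the range from correlation 0 to 0.9 is 18.5% to 9.4%, and 9.6% to 4.7% favouring Imupret.

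**4. Build in the known overlap.** The synopsis counts treatment as effective only if there is no antibiotic indication, so the tests cannot be independent. I simulated identical arms of 100 with that rule and pooled z tests, in 24 scenarios of 20,000 trials. Assumed inputs:

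- antibiotic use 15%, 25% or 40%;
- symptom cut met by 20% or 50% at visit 2 and by 85% or 95% at visit 4;
- latent correlation 0.3 or 0.7.

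Any false p < 0.05 occurred in 8.5% to 12.8% of trials, and one favouring Imupret in 4.2% to 6.4%. Single tests ran at 4.7% to 6.0%, so the excess comes mainly from multiplicity.

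**5. Does another sentence fix the analysis earlier?** The SAP's promise to settle technical details before data analyses is compatible with settling them after closure, and does not place them before arm-level data can be seen. The SAP is dated 07.02.2019, close to the planned first patient, but it defers the specifications itself. A blind data review meeting appears only in the abbreviation list, and no such procedure is described.

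**The case against.** The strongest reply is that the trial is exploratory by its own account. The word stands in the synopsis design line, Protocol 8.1, 8.2 and 12.2, and the SAP, while the superiority text sits in one box of the synopsis. On that reading no 5% claim exists to be broken. The confirmation wording in Protocol 6.1 and 6.3 can be read as background rationale. This is fair as far as it goes: the loss of error control is conditional on keeping the superiority claim. The contradiction remains, and the exploratory reading requires that claim to be withdrawn.

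Second, some text limits the freedom. Both documents follow ICH E9 and plan one main evaluation, and Protocol 12.1 has the analysis sets documented by database lock. The synopsis also identifies a main variable, on which the trial was sized. These narrow the choices, but none fixes the test, the decision visit or the standing of antibiotic need as a second main criterion.

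Third, the percentages are illustrations, which is correct. The 40% antibiotic scenarios fit badly with Table 1: at most 60% of patients could then be effective, against the assumed 75% in controls. They supply the low end of the simulated range. The 15% scenarios sit closer to Table 1 and give about 11% to 13%, so removing the poor fits raises the estimate. The synopsis also plans local-scale comparisons at visit 3, which would add a test.

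**Conclusion.** The concern holds, and it must be fixed if the superiority claim is to stand. A rule that specifies the analysis after closure of an unblinded database, with data-driven tests and optional correction, does not deliver the two-sided 5% error rate used to size the trial.

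For three uncorrected main tests the familywise error is about 8% to 14%, and about 4% to 7% in favour of Imupret against 2.5%. These figures rest on the assumed number of tests, correlations and antibiotic rates. A scored visit 3 or repeats in the per-protocol set would raise them. The main conclusion needs none of these assumptions, because the documents set no limit on the choices. If the trial is declared exploratory throughout, no error rate is broken, but no superiority claim can be made.

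**What to change.** Choose one of two routes.

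**(a) Keep the superiority claim.** In Protocol 12.2 and the SAP, replace the timing and data-driven sentences with: *The analysis is specified in a signed SAP before database closure and before any summary by arm.* Because the trial is open, closure is the latest acceptable date and earlier is better. That SAP should contain:

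- one primary endpoint, one decision visit and one test of zero difference at two-sided 0.05 with a 95% confidence interval, with the synopsis hypothesis amended to match, since only that null reproduces 97 per group;
- the order or alpha split of the two main criteria, for example the dichotomous main variable at visit 4, then antibiotic need in fixed sequence. The reverse order is equally open, since antibiotic need is the first listed objective;
- as primary set, all randomised patients with a post-baseline value. The present full analysis set requires an application of IMP, which controls cannot meet;
- patients with an antibiotic indication kept in that set and counted as not effective, as the synopsis defines. The separate evaluation in Protocol 8.3.3 and 10.2 is then additional;
- all other visits, endpoints and data-driven analyses labelled exploratory, with no superiority claim.

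Delete the statement that there is no formal sample size estimation, and reconcile the synopsis design line and Protocol 8.1 and 8.2 with the sample size section.

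**(b) Report as exploratory.** Withdraw the superiority wording in the synopsis and the confirmation wording in Protocol 6.1 and 6.3.

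**Cost.** Either route takes a protocol amendment and a SAP revision, with no new patients or data. On the planned dates (last patient out about December 2019) this fits before closure. Route (a) reduces freedom in choosing tests. In a fixed sequence, the second claim depends on the first. An equal alpha split lowers power for the main variable at 97 per group from 80.1% to Φ(2.804 − 2.241) = 71.3%.
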